2.2 Study Endpoints

2.2.1 Primary Endpoint

The primary endpoint is change from baseline in pathological findings in colon biopsies after the first 28 days of neratinib monotherapy.

2.2.2 Secondary Endpoints

The secondary endpoint will be the incidence and severity of diarrhea during the first 28-day cycle of neratinib monotherapy.

2.3 Overall Study Design and Plan

2.3.1 Study Design

This is an open-label, phase 2 study that will investigate colon pathology in patients with HER2-positive breast cancer treated with neratinib as monotherapy.

All patients will receive neratinib for the first 28 days as a single daily dose of 240mg.

Following the second study colonoscopy procedure:

- For patients being treated for stage 1 to 3c breast cancer in the extended adjuvant setting, neratinib will continue to be administered at a single daily dose of 240mg until completion of one year of therapy from start of treatment , or until disease

recurrence (as determined by the Investigator), death, unacceptable toxicity, or other specified withdrawal criterion.

- For patients being treated for metastatic breast cancer (mBC), capecitabine will be introduced after the second study colonoscopy procedure at a dose of 750mg/m² twice daily for 14 days of each 21 day treatment cycle, with neratinib administered continuously throughout at 240mg daily, until disease progression, death, unacceptable toxicity, or other specified withdrawal criterion.

All patients will receive loperamide diarrhea prophylaxis daily for one (1) 28-day cycle and then as needed.

Following a 28-day screening period, eligible patients will be enrolled. Baseline assessments will be performed prior to Cycle 1/Day 1 dosing. Patients will then participate in the active treatment phase, consisting of, in both groups, a single 28-day cycle of neratinib monotherapy. Neratinib and loperamide will be administered orally by patients. The morning dose of neratinib will be held on the day of the second study colonoscopy procedure.

Colonoscopy will be performed after eligibility has been confirmed, but prior to administration of the first dose of neratinib on Day 1 of Cycle 1, and at Day 30 (\pm 3 days). Thereafter, extended adjuvant patients with stage 1 to 3c breast cancer will continue to receive neratinib monotherapy for 1 year or until progression of disease, death, or intolerance to study prescribed therapy. Patients with mBC will continue to receive neratinib in 21-day cycles, beginning in Cycle 2, after completion of the second study colonoscopy procedure, in combination with capecitabine administered on Day 1-14 of each cycle, until progression of disease, death, or intolerance to study prescribed therapy.

NOTE; patients with mBC cannot be exposed to capecitabine until after completion of the second study colonoscopy procedure.

In extended adjuvant patients with stage 1 to 3c breast cancer, patients will return to the clinic approximately every 3 months for safety assessments. End of Treatment (EOT) visit is planned on upon completion of 1 year of treatment, followed by Safety Follow-up Visit 28 days after the last dose of neratinib.

In patients with mBC, clinic visits during the active treatment phase are planned on Day 1 of Cycle 1, Cycle 2, and each subsequent cycle. Treatment discontinuation visit is planned 0-3 days after the last dose, followed by a Safety Follow-up Visit 28 days after the last dose of neratinib.

The study will end when all patients have been followed-up for 28 days after the last dose of neratinib.

Approximately 3-5 patients will be enrolled at approximately 2 centers.

The approximate duration of the study is 1.5 years.

Patients with stage 1 to 3c disease receiving extended adjuvant therapy are anticipated to participate in the study for approximately 1 year. This includes 1 month for screening, approximately 12 months for the active treatment phase until progression of disease or intolerance to study prescribed therapy, and safety follow-up visit 28 days after the last dose of neratinib.

Patients with mBC are anticipated to participate in the study for an average of 12 months. This includes approximately 1 month for screening, an estimated average of 9.5 months for the active treatment phase, and an estimated average of 1 month for initial Safety Follow-up. Patients who permanently discontinue treatment due to unacceptable toxicity will be followed-up for 28 days after the last dose of neratinib to collect any adverse events (AEs) (Section 9.4).

The primary analysis will be conducted after all patients have completed two sets of colon biopsies. The final analysis will be conducted when all patients with stage 1 to 3c breast cancer have completed 1 year of study treatment or have met other specified withdrawal criteria and patients with mBC have discontinued therapy or have met other specified withdrawal criteria.

The study will end when all patients have been followed up for 28 days after the last dose of neratinib.

In the event that end of treatment (EOT) is declared earlier by the Sponsor, patients will be offered the opportunity to complete treatment through a treatment extension study.

2.3.2 Neratinib Adjustments

Neratinib may be dose-adjusted/reduced due to neratinib-related toxicity. The prescribed dose levels can be 240mg, 200mg, 160mg, 120mg, with the latter three doses representing the reduction levels. If doses of neratinib are held, study procedures for that cycle will proceed on schedule as planned, without any delay. Missed dose(s) of neratinib (i.e., any dose that is not administered within the protocol-defined administration window) will not be made up. **Note: Patients should take one dose per calendar day.** The dose adjustment guidelines represent the minimum set of measures the Investigator must follow. However, additional measures may be taken, as necessary, for certain patients per the Investigator's medical judgment. All dose modifications/adjustments should be documented in the patient's source file.

Once the neratinib dose has been reduced for a patient, all subsequent cycles must be administered at that dose, unless further dose reduction is required. Dose re-escalation will only be permitted if explicitly approved in advance by the Sponsor. Evidence of this approval must be contained within the patient's source file.

Patients must discontinue the investigational product if a criterion for withdrawal is met. Reintroduction of the discontinued investigational product at a later time during the active treatment phase is not permitted.

2.3.3 Loperamide

- The initial dose of loperamide 4 mg will be self-administered orally with the first dose of neratinib.
- During weeks 1-2 (day 1 – 14) of Cycle 1 loperamide 4 mg will be self-administered three time daily.
- During weeks 3-4 (days 15 – 28) of Cycle 1 loperamide 4 mg will be self-administered twice daily
- After the first 28 days, loperamide will be self-administered as needed (PRN) (not to exceed 16 mg per day).

2.3.4 Loperamide Dose Adjustments

Patients are expected to take loperamide prophylaxis as directed. However, patients may require individualization of loperamide prophylaxis dose (up to a maximum dose of 16 mg per day).

- For patients who develop diarrhea during Cycles 1, loperamide should be increased up to a maximum of 16 mg a day.
- If a patient is unable to tolerate loperamide due to symptomatic constipation, loperamide should be held until after the first bowel movement and then resumed at a dose reduced by one level.
- For recurrent symptomatic constipation events, hold loperamide until after the first bowel movement and then resume at a dose reduced to the next lower dose level.
- If a patient is unable to tolerate once-daily loperamide due to constipation, hold loperamide and discuss subsequent loperamide dosing with the Medical Monitor.
- Neratinib dosing should continue if loperamide is held.

Loperamide dose reduction levels for constipation are:

- Dose Level 0 (4mg TID or 6 tablets/capsules a day)
- Dose Level -1 (4 mg BID or 4 tablets/capsules a day)
- Dose Level -2 (2mg TID or 3 tablets/capsules a day)
- Dose Level -3 (2 mg BID or 2 tablets/capsules a day)
- Dose Level -4 (2 mg once a day or 1 tablet/capsule a day)

If a patient experiences an AE leading to dose interruption of neratinib for reasons other than diarrhea, consider holding loperamide until neratinib treatment is resumed.

2.3.5 Capecitabine

Patients with mBC will receive capecitabine, beginning in Cycle 2 of treatment (i.e., following completion of the second study colonoscopy procedure and biopsy).

Capecitabine is available at 150 mg and 500 mg film-coated tablets.

Capecitabine (total dose of 1500 mg/m² daily, administered as 750 mg/m² in approximately evenly divided doses) will be self-administered orally by patients starting with Cycle 2/Day 1 (i.e. following completion of the second study colonoscopy procedure and biopsy). Doses are to be taken daily on Days 1 to 14 of each 21-day cycle. Capecitabine should be taken with water within 30 minutes after a meal.

During treatment with neratinib plus capecitabine, patients should be monitored for conditions that may require dose to be held or discontinued. Careful attention should be paid to the onset of diarrhea or hand-foot syndrome in particular, and early dose adjustment or prophylactic therapy should be implemented.

Daily dose of neratinib plus capecitabine should continue until a criterion for treatment withdrawal or study withdrawal is met.

2.3.6 Capecitabine Dose Adjustment

Recommended dose reductions for capecitabine-related toxicity in combination with neratinib are listed below:

Dose Level	Capecitabine (administered in combination with neratinib)
Starting Dose	1500 mg/m ² , 750 mg/m ² BID
-1 ^{aa}	1100 mg/m ² , 550 mg/m ² BID
-2 ^a	750 mg/m ² , 375 mg/m ² BID

2.4 Study Population

Approximately 3-5 patients will be enrolled.

3. DEFINITIONS

Baseline

The baseline value for a parameter of interest is the last measurement obtained prior to or on the date of the first dose of neratinib.

Cycle

The first cycle is 28 days for all subjects, all of whom receive neratinib and loperamide prophylaxis. After the first 28-day cycle, stage 1 to 3c breast cancer patients receiving extended adjuvant treatment return to clinic every 3 months. Metastatic breast cancer patients return to clinic at scheduled 21-day cycles, during with time they receive both neratinib and capecitabine.

Study Day 1

Study Day 1 is the date the first dose of neratinib is taken.

Treatment duration

Treatment duration in days = last dose date - first dose date + 1

Actual Dose Intensity

The actual dose intensity is defined as the cumulative actual dose divided by treatment duration.

Relative Actual Dose Intensity

The relative actual dose intensity is defined as the actual dose intensity divided by the planned dose intensity.

Prescribed Dose Intensity

The prescribed dose intensity is defined as the cumulative prescribed dose divided by treatment duration.

Treatment-Emergent Adverse Event (TEAE)

A TEAE is defined as an AE that occurs or worsens on or after the first administration of neratinib and up to 28 days after the second colonoscopy in patients with stage 1 to 3c breast cancer, and following completion of Cycle 2 in mBC patients.

Investigational Product (IP)

Investigational product (IP) is used to reference neratinib and capecitabine.

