6.7.2 Study Medication (Capecitabine)

A listing will be provided for capecitabine exposure, which will include treatment duration (months), cumulative actual dose (mg/m²), actual dose intensity (mg/m²/day), relative actual dose intensity (%).

Indicator for dose reduction (yes/no) and dose reduction due to AE (yes/no) and the lowest dose reduction level will be included in the listing. In addition, indicator for dose withheld due to AE (yes/no) will be included.

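### Capecitabine dose intensity leaves out the last rest week and has no stated planned rate, so the listed value shifts with cycle count and relative intensity cannot be reproduced

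*SAP*

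**What the plan says.** SAP 3 (Definitions) has a single rule for treatment duration, with no version for any particular drug: "Treatment duration in days = last dose date - first dose date + 1". Two further definitions build on it: "The actual dose intensity is defined as the cumulative actual dose divided by treatment duration", and "The relative actual dose intensity is defined as the actual dose intensity divided by the planned dose intensity".

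SAP 6.7.2 applies these to capecitabine. Its exposure listing includes treatment duration, cumulative dose, and "actual dose intensity (mg/m²/day), relative actual dose intensity" as a percentage. It also carries indicators for dose reduction, reduction due to an adverse event and dose withheld due to an adverse event, and the lowest dose level reached.

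The schedule is in SAP 2.3.5: "Capecitabine (total dose of 1500 mg/m² daily", with "Doses are to be taken daily on Days 1 to 14 of each 21-day cycle". The first reduced level, in SAP 2.3.6, is "1100 mg/m ² , 550 mg/m ² BID".

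The SAP works out a planned dose intensity for one drug only, loperamide (SAP 6.8.1). It gives none for capecitabine.

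**The concern.** A duration that runs from first to last dose suits a drug taken every day, such as neratinib. It does not suit one taken for 14 days and then rested for 7. The rest weeks between cycles fall inside the interval, but the one after the final tablet does not. The denominator is therefore always 7 days short of whole cycles, and the relative effect depends on how many cycles the patient completed. Two patients who both took every planned tablet get different actual dose intensities if one stayed longer.

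Relative dose intensity has a second problem. It needs a planned rate, and a programmer has to choose one. The plausible choices give different answers for the same patient, and they err in opposite directions.

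What is at stake is how the capecitabine exposure listing reads. SAP 6 presents data as listings unless otherwise indicated, so the listed percentage is itself the reported result. Data are also shown at the primary analysis, which follows the last patient's second colonoscopy. Because each patient starts capecitabine only after her or his own second colonoscopy, recently enrolled metastatic patients may then have few cycles, which is where the distortion is largest.

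**Working it through.** **Inputs.** Starting dose 1500 mg/m² per dosing day, Days 1-14 of 21 (SAP 2.3.5); level −1 is 1100 mg/m² per dosing day (SAP 2.3.6); duration and intensity formulas from SAP 3; average active treatment of 9.5 months for metastatic patients, including the 28-day Cycle 1 without capecitabine (SAP 2.3.1).

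**The plan's own figure.** Loperamide, SAP 6.8.1: (12 × 14 + 8 × 14)/28 = 280/28 = 10 mg/day. This reproduces exactly. It averages the planned dose over all calendar days of the cycle.

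**Duration.** With k completed cycles and no delays, the last dose falls on day 21(k − 1) + 14, so the SAP duration is 21k − 7 days.

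**Actual dose intensity, full adherence.** Cumulative dose is 14 × 1500 × k = 21,000k mg/m². Dividing by 21k − 7 gives the fourth column. The last two columns divide that by two candidate planned rates: the cycle average, 1500 × 14/21 = 1000 (assumed, on the loperamide pattern), and the dosing-day dose, 1500.

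| Cycles k | SAP duration (days) | Cumulative dose (mg/m²) | Actual intensity (mg/m²/day) | Relative to 1000 | Relative to 1500 |
|---|---|---|---|---|---|
| 1 | 14 | 21,000 | 1500 | 150.0% | 100.0% |
| 2 | 35 | 42,000 | 1200 | 120.0% | 80.0% |
| 3 | 56 | 63,000 | 1125 | 112.5% | 75.0% |
| 6 | 119 | 126,000 | 1058.8 | 105.9% | 70.6% |
| 12 | 245 | 252,000 | 1028.6 | 102.9% | 68.6% |

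Over whole cycles the intensity is 21,000k/21k = 1000 mg/m²/day for every k.

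**A third reading.** If planned cumulative dose is divided by the same SAP duration, the durations cancel and full adherence reads 100% at every k.

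**A reduced patient.** One cycle at 1500, then one at 1100: 14 × 1500 + 14 × 1100 = 36,400 mg/m². The SAP intensity is 36,400/35 = 1040 mg/m²/day, which is 104% of 1000 or 69.3% of 1500. The share of planned dose actually taken is 36,400/42,000 = 86.7%.

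**Typical size.** Against 1000, the excess under full adherence is 7/(21k − 7). With 30-day months, 9.5 months is 285 days; (285 − 28)/21 = 12.2 cycles. At 12 cycles the excess is 7/245 = 2.9 percentage points.

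**Check of the remedy.** With duration 21k and planned rate 1000, full adherence reads 100% at every k, and the reduced patient reads (36,400/42)/1000 = 86.7%. Changing duration alone is not enough: against 1500, full adherence would read 1000/1500 = 66.7%. Truncating duration at data cut-off against a fixed 1000 is not enough either: a patient cut off on capecitabine day d ≤ 14 has 1500d/d = 1500, or 150%. Dividing by planned dose to the same date gives 1500d/1500d = 100%.

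**The case against.** The strongest reply is that the SAP states no wrong number. A reader might infer that a perfectly adherent patient will be listed at 150% after one cycle, or that a dose-reduced patient will be listed above 100%. Neither follows from the SAP alone. Both need a planned rate of 1000 mg/m²/day, which the SAP never gives for capecitabine. Against 1500, the only daily starting dose it states for the drug, one full cycle reads 100% and the example reduced patient reads 69.3%. If planned and actual dose share the same duration, the distortion in relative intensity disappears; SAP 3 builds the neighbouring prescribed dose intensity over that duration. This part of the reply stands, so the percentages here are conditional.

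Two other inferences also go too far. The measure does not overstate for everyone, since the 1500 reading understates after the first cycle. Nor does it hide reduced dosing: at two cycles against 1000, full dosing reads 120% and the 1500-then-1100 patient 104%, and the same listing shows cumulative dose, reduction indicators and lowest dose level.

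The reply does not remove the effect on actual dose intensity. That follows from stated rules, with no assumed planned rate: 1500, 1200, then 1125 mg/m²/day for unchanged, perfect adherence. Nor does it supply the missing planned rate.

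**Conclusion.** The point holds, as a minor one. For completed cycles without delays, the SAP's duration rule makes capecitabine's actual dose intensity depend on the number of cycles: 50% above the whole-cycle average after one and 2.9% above it after 12. Relative dose intensity cannot be reproduced, because its denominator is undefined. For a fully adherent patient with one to 12 cycles, the two fixed candidate rates give 150% down to 102.9%, or 100% down to 68.6%. The cycle average of 1000 is the more natural choice given the loperamide example, but it remains an assumption.

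The reach is small. Only metastatic patients among the 3-5 enrolled are affected, in a per-patient listing; SAP 9.1 plans no exposure table. No primary or secondary endpoint is involved. Neratinib is dosed continuously and has no planned rest week, so this does not apply to it.

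**What to change.** In SAP 3 and 6.7.2, define both terms for capecitabine together:

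- **Treatment duration:** start date of the last capecitabine cycle + 20 days − date of first capecitabine dose + 1, so that whole 21-day cycles are counted.
- **Planned dose intensity:** 1500 × 14/21 = 1000 mg/m²/day, written out as SAP 6.8.1 does for loperamide.
- **Cycles cut short by death or data cut-off:** relative dose intensity = cumulative actual dose divided by cumulative planned dose, both to that same date.

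The cost is a few lines of text and one extra derivation; no data collection or treatment changes. The drawback is that a patient who stops early within a cycle reads lower. For example, 5 full-dose days in a single cycle give 7500/21 = 357 mg/m²/day, or 35.7%. That is a convention to be stated, and the cumulative dose beside it lets the reader see why.

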4. INVESTIGATIONAL PLAN

4.1. Overall Study Design

This is an open-label, phase 2 study that will investigate colon pathology in patients with HER2-positive breast cancer treated with neratinib as monotherapy.

All patients will receive neratinib for the first 28 days as a single daily dose of 240mg.

Following the second study colonoscopy procedure:

- For patients being treated for stage 1 to 3c breast cancer in the extended adjuvant setting, neratinib will continue to be administered at a single daily dose of 240mg until completion of one year of therapy from start of treatment, or until disease recurrence (as determined by the Investigator), death, unacceptable toxicity, or other specified withdrawal criterion.
- For patients being treated for metastatic breast cancer (mBC), capecitabine will be introduced after the second study colonoscopy procedure at a dose of 750mg/m² twice daily for 14 days of each 21 day treatment cycle, with neratinib administered continuously throughout at 240mg daily, until disease progression, death, unacceptable toxicity, or other specified withdrawal criterion.

All patients will receive loperamide diarrhea prophylaxis daily for one (1) 28-day cycle and then as needed.

Following a 28-day screening period ([Section 9.1](#)), eligible patients will be enrolled. Baseline assessments will be performed prior to Cycle 1/Day 1 dosing. Patients will then participate in the active treatment phase, consisting of, in both groups, a single 28-day cycle of neratinib monotherapy ([Section 9.2](#)). Neratinib and loperamide will be administered orally by patients as described in [Section 6](#). The morning dose of neratinib will be held on the day of the second study colonoscopy procedure ([Section 6.1](#)).

Colonoscopy will be performed after eligibility has been confirmed, but prior to administration of the first dose of neratinib on Day 1 of Cycle 1, and at Day 30 (\pm 3 days). Thereafter, extended adjuvant patients with stage 1 to 3c breast cancer will continue to receive neratinib monotherapy for 1 year or until progression of disease, death, or intolerance to study prescribed therapy. Patients with mBC will continue to receive neratinib in 21-day cycles, beginning in Cycle 2, after completion of the second study colonoscopy procedure, in combination with capecitabine administered on Day 1-14 of each cycle, until progression of disease, death, or intolerance to study prescribed therapy.

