4.2. Study Duration and Termination of Study

The approximate duration of the study is 1.5 years.

Patients with stage 1 to 3c disease receiving extended adjuvant therapy are anticipated to participate in the study for approximately 1 year. This includes 1 month for screening, approximately 12 months for the active treatment phase until progression of disease or intolerance to study prescribed therapy, and safety follow-up visit 28 days after the last dose of neratinib.

Patients with mBC are anticipated to participate in the study for an average of 12 months. This includes approximately 1 month for screening, an estimated average of 9.5 months for the active treatment phase, and an estimated average of 1 month for initial Safety Follow-up. Patients who permanently discontinue treatment due to unacceptable toxicity will be followed-up for 28 days after the last dose of neratinib to collect any adverse events (AEs) ([Section 9.4](#)).

The primary analysis will be conducted after all patients have completed two sets of colon biopsies. The final analysis will be conducted when all patients with stage 1 to 3c breast cancer have completed 1 year of study treatment or have met other specified withdrawal criteria and patients with mBC have discontinued therapy or have met other specified withdrawal criteria (see [Section 10](#)).

The study will end when all patients have been followed up for 28 days after the last dose of neratinib.

In the event that end of treatment (EOT) is declared earlier by the Sponsor, patients will be offered the opportunity to complete treatment through a treatment extension study.

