12.3. Safety Analyses

All patients who receive a dose of neratinib will be analyzed for safety. The incidence of TEAEs and SAEs for Cycle 1 through 28 days of neratinib monotherapy following the second study colonoscopy procedure in patients with stage 1 to 3c breast cancer treated in the extended adjuvant setting, and following the completion of Cycle 2 in patients with mBC will be summarized after all biopsies have been completed. Following 28 days of neratinib monotherapy after the completion of the second study colonoscopy procedure in patients with stage 1 to 3c breast cancer treated in the extended adjuvant setting, and Cycle 2 in patients with mBC through 28 calendar days after the last administration of neratinib, only SAE data will be collected and summarized.

AEs will be coded using the Medical Dictionary for Regulatory Activities MedDRA coding system and all AEs will be graded by the Investigator according to the NCI-CTCAE version 4.0.

Incidence of AEs will be summarized by system organ class (SOC) and preferred term (PT), and will be summarized by grade. A patient who experiences the same AE more than once within a SOC or preferred term category will be counted only once, using the worst toxicity grade for that event. SAEs will be summarized.

Serious AE and deaths will be provided in a listing. All AEs resulting in discontinuation of neratinib in Cycle 1 through 28 days of neratinib monotherapy following the second study colonoscopy procedure in patients with stage 1 to 3c breast cancer treated in the extended adjuvant setting, and following the completion of Cycle 2 in patients with mBC, dose modification, dosing interruption, and/or treatment delay of investigational product will also be listed and tabulated by PT.

Laboratory test results will be collected at screening and on Day 1/Cycle 1 and Cycle 2. On-study laboratory test abnormalities reported during screening, Cycle 1 and Cycle 2 will be summarized. In subsequent visits only liver function tests will be collected.

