Abbreviations: β-hCG=beta-human chorionic gonadotropin; ALP=alkaline phosphatase; ALT=alanine aminotransferase; AST=aspartate aminotransferase; BUN=blood urea nitrogen; C=cycle; CBC=complete blood count; CRP = C-reactive protein; D=day; ECG= electrocardiogram; ECHO=echocardiogram; ECOG=Eastern Collaborative Oncology Group; eCRF=electronic case report form; EOT = end of treatment; ESR = erythrocyte sedimentation rate; FISH= fluorescence in situ hybridization; Hb=hemoglobin; Hct=hematocrit; IHC=immunohistochemistry; INR = International Normalized Ratio; LFT=liver function test; LDH=lactate dehydrogenase; MUGA=multiple-gated acquisition scan; NP=nurse practitioner; PA=physician's assistant; RBC=red blood cell; SAE=serious adverse event; TEAE=treatment-emergent adverse event; WBC=white blood cell.

^a Cycle 1, neratinib monotherapy, is defined as 28 days. Cycle 2 and all subsequent cycles are defined as 21 days. Cycle 2 will begin after the completion of the second study colonoscopy procedure. The Treatment Discontinuation Visit will be performed as soon as possible, but no later than 3 business days after the last dose and before start of new anticancer regimen. All visit dates are calculated from the date of first dose of neratinib. If a visit occurs before or after a scheduled visit date, the next visit is still expected to occur on the date initially calculated for this visit, and is not shifted due to an earlier or later prior visit.

^b Screening procedures and enrollment may occur on one day, however, enrollment must not be done before all screening procedures have been completed and results confirming eligibility have been reviewed.

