6.9.2 Treatment-Emergent Adverse Events (TEAEs)

A high-level summary of TEAE will be provided and select summaries of TEAE subgroups (indicated in parentheses).

TEAEs will also be presented in incidence tables by system organ class (SOC), preferred term (PT), and grade for the following:

- Any TEAE (summary)
- Treatment-related TEAE
- Serious TEAE
- Serious treatment-related TEAE
- Grade 3 or 4 TEAE (summary)
- Fatal TEAE (summary)
- TEAE leading to dose reduction
- TEAE leading to dose interruption
- TEAE leading to treatment discontinuation

Incidence tables of TEAEs in descending order of frequency by PT will be presented for any TEAE, Grade 3 or 4 TEAE, and fatal TEAE.

Listings will be provided for SAEs, TEAEs, and TEAEs leading to study drug discontinuation.

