9. LIST OF PLANNED TABLES, FIGURES, AND LISTINGS

9.1 TABLES

Tables
Summary of treatment-emergent diarrhea characteristics
TEAE (high-level summary)
TEAE by SOC, PT, and Grade
Grade 3 or 4 TEAE by SOC, PT, and Grade
Fatal TEAE by SOC, PT, and Grade
TEAE in descending order of incidence by PT
Grade 3 or 4 TEAE in descending order of incidence by PT
Fatal TEAE in descending order of incidence by PT
AESI by event category, PT, and Grade
Incidence of liver function test abnormality

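### The SAP's serious and fatal tables stop at the short TEAE window, so SAEs and deaths later in the collection period are listed but not summarized as Protocol 12.3 promises

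*SAP*

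**What the plan says.** **The window.** SAP section 3 defines a TEAE as an event that starts or worsens on or after the first neratinib dose. It gives the end of the window as "up to 28 days after the second colonoscopy in patients with stage 1 to 3c breast cancer, and following completion of Cycle 2"; the Cycle 2 limb applies to the mBC group. No second window is defined for serious or fatal events.

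**The tables.** SAP 6.9 centres its adverse event summaries on TEAEs. The incidence tables in SAP 6.9.2, including the serious, serious treatment-related and fatal ones, are all subsets of TEAEs, and so is the high-level summary. SAP 9.1 repeats this with entries such as "Fatal TEAE by SOC, PT, and Grade". It has no entry for the serious table that 6.9.2 promises.

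**The protocol.** Once the short window has closed, Protocol 12.3 says that "through 28 calendar days after the last administration of neratinib, only SAE data will be collected and summarized". The synopsis and Protocol 8.2.1 say the same. Protocol 12.3 also says, as a separate commitment, that serious events and deaths will be listed.

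**Declared changes.** SAP section 8 is marked not applicable.

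**The listings.** SAP 6.9.2 and 9.2 plan an SAE listing that is not limited to TEAEs. SAP 6.9.4 plans a death listing with a flag for death within 28 days of the last neratinib dose. Listings are the SAP's default presentation (section 6) and, with narratives, the main one in the protocol synopsis.

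**The concern.** The protocol commits to a summary of late SAEs, the SAP does not provide one, and the SAP does not declare the difference.

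Take a patient who has an SAE, or dies, on neratinib in month 4. The event is collected. The death listing would flag the death as on-study. Neither event would be a TEAE, so neither would appear in the serious or fatal tables or in the high-level summary. If it were the only such event, the table would show zero. With 3 to 5 patients, one event is between 1/5 = 20% and 1/3 = 33% of the planned enrolment.

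The final analysis does little to help. The primary analysis follows the last second colonoscopy. After that, the serious and fatal tables can gain only what is left of each patient's short window, although SAE follow-up continues for most of a year in patients who stay on treatment.

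**Working it through.** The documents state no coverage figure to reproduce, so this is a day count.

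**Inputs**
- Second colonoscopy: Day 30 ± 3, that is Day 27 to 33 (SAP 2.3.1). The notes to Protocol Table A1.2 instead give Day 1 of Cycle 2 plus up to 5 days for mBC. With a 28-day Cycle 1 the latest day is 29 + 5 = Day 34.
- Stage 1 to 3c treatment: "until completion of one year of therapy from start of treatment" (Protocol 4.1), taken as 365 days.
- mBC treatment: "an estimated average of 9.5 months for the active treatment phase" (Protocol 4.2).
- mBC Cycle 2: 21 days, and "Cycle 2 will begin after the completion of the second study colonoscopy procedure" (Protocol Appendix 1).
- End of SAE collection: last neratinib dose + 28 days (Protocol 12.3).

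**Formula.** Share after the window = (E − W) / E, where E is the last day of SAE collection and W the last day of the TEAE window, both counted from first dose.

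**Stage 1 to 3c, full year.** E = 365 + 28 = 393.

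| Colonoscopy | W | Share after W |
|---|---|---|
| Day 27 | 27 + 28 = 55 | 338/393 = 86.0% |
| Day 30 | 30 + 28 = 58 | 335/393 = 85.2% |
| Day 33 | 33 + 28 = 61 | 332/393 = 84.5% |

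**mBC, average duration.** E = 9.5 × 30.44 + 28 ≈ 317. A 21-day Cycle 2 ends 20 days after the colonoscopy if it starts that day, or 21 days after if it starts the next day.
- Earliest: W = 27 + 20 = 47, share = 270/317 ≈ 85%.
- Latest on Day 30 ± 3: W = 33 + 21 = 54, share = 263/317 ≈ 83%.
- Latest on the Table A1.2 timing: W = 34 + 21 = 55, share = 262/317 ≈ 83%.

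**Early stopping, stage 1 to 3c** (E = last dose day + 28, W = 55 to 61)

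| Last dose | E | Share after W |
|---|---|---|
| Day 180 | 208 | 71-74% |
| Day 90 | 118 | 48-53% |
| Day 60 | 88 | 31-38% |
| Day 30 | 58 | 0-5% |

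**Counting from consent.** Protocol 13.2 starts reporting at consent. If consent is assumed 28 days before Day 1, the stage 1 to 3c total is 393 + 28 = 421 days, of which 332/421 = 79% to 338/421 = 80% falls after the window.

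**After the change.** With the serious and fatal tables run to last dose + 28 days, W equals E and the share after the window is 0%.

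**The case against.** The best defence is that for 3 to 5 patients the listings are the report. The synopsis makes listings and narratives the primary presentation and summary statistics optional, and SAP section 6 defaults to listings. Every late SAE and death appears there, with the death flag already set at 28 days after last dose. The short TEAE window also has a source: Protocol 12.3 first asks for TEAEs and SAEs to be summarized over that early period. It does not say what form the later SAE summary must take. No test or decision rule depends on these tables.

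Most of this stands, and it limits the severity. It does not remove the point. Protocol 12.3 promises both a summary and a listing, and a listing meets only the second. SAP section 6 allows exceptions to its listing default, and 6.9.2 makes one by specifying tables.

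A reader might infer more than the documents support:
- **That late events go unreported.** They do not; they are listed. Some might also enter the adverse events of special interest table, which SAP 6.9.3 words to cover all such events, although 6.9 points towards TEAEs.
- **That the tables would contradict the listings.** A fatal TEAE table with a defined window and a listing of all deaths differ in scope. They could differ under any window, because Protocol 13.1.3 does not allow disease progression to be recorded as an adverse event term. The risk is a misread zero, which is why the window needs a label.
- **That the discontinuation table departs from the protocol too.** It does not. Protocol 12.3 itself confines that tabulation to the early period.

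**Conclusion.** The point holds as an undeclared mismatch between Protocol 12.3 and the SAP, and should be fixed. As written, SAEs and deaths after about Day 55-61 (stage 1 to 3c) or about Day 47-55 (mBC) enter no serious or fatal summary table, although they are collected and listed.

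The size is about 83-86% of SAE collection time after first dose. That rests on a full year of treatment for stage 1 to 3c and on the 9.5-month average for mBC, and it falls with early stopping. It is a share of calendar time. A reader might take it as the share of SAEs that would be missed, but the documents give no SAE timing that would support that.

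The mBC range also assumes that the SAP's Cycle 2 clause means the window ends when Cycle 2 ends, which the wording leaves unclear.

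**What to change.** 1. In SAP section 3, keep the short window for non-serious events and add a rule of this kind: *for serious and fatal adverse events, treatment-emergent means onset or worsening from the first dose of neratinib through 28 days after the last dose.*
2. Run the serious and fatal tables, and the matching rows of the high-level summary, on that window. State the window in every table title.
3. Add to SAP 9.1 the serious-event table that 6.9.2 promises.
4. While editing the definition, state the mBC end date plainly, and name the date that closes the short window for a stage 1 to 3c patient who has no second colonoscopy. At present that patient has no anchor.

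If the sponsor prefers not to tabulate late events, the minimum is a statement in SAP section 8 that SAEs and deaths after the TEAE window are listed only, plus the window labels.

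The cost is a few lines of SAP text, one derived flag and one table shell. No new data are needed. It should be done before database lock, by which time SAP section 1 requires the SAP to be final.
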